
Section 7.1 Screening, Recruitment, and Informed Consent                  Section 7.7 Temporary Measures (Procedures Related to the COVID Pandemic)
	
Integrated protocol amendment 7 addendum previously created to describe temporary measures applied during the COVID pandemic. Additional update to these temporary measures to clarify that radiographic assessments are required for subjects <math>\geq 14</math> years (who were skeletally immature at their last assessment) as part of the minimal safety procedures
	
To integrate protocol amendment 7 for addendum. To assess skeletal maturity in subjects <math>\geq 14</math> years re-initiating treatment in order to ensure appropriate safety follow up as well as determine if weight-based dosing is required.

	prior to re-initiation of palovarotene.	
Changes that did not affect the clinical conduct of the study:		
Table 3	Removed ECG row that was included in error; correcting table and footnotes.	Integration of administrative change from protocol amendment 7 addendum.
Section 7.6	Added DMC language.	Clarifying DMC oversight
Section 9.1.10 Follow up of Adverse Events and Serious Adverse Events	Collection of SAE reports, including deaths, will continue until 30 days past end of study.	Clarification of end date of collection of SAE, including death reports.
General	Corrected minor errors and formatting irregularities.	To provide a consistent presentation.

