- 4 Non-flare-up Day 1 is the first day that non-flare-up-based treatment was initiated during Part B, and total duration of treatment will continue into Part C. Subjects who began non-flare-up-based treatment during Part B will continue the same visit schedule into Part C, and will receive non-flare-up-based treatment for up to an additional 48 months. Therefore, these subjects may undergo non-flare-up-based treatment for up to 72 months over the entire study. Subjects who decide to stop treatment more than 1 month after an annual visit but who remain in the study will undergo all assessments included in an annual visit as part of their EOT assessments. If the next annual visit is in less than 6 months, the EOT will serve as their EOS assessments and will conclude their participation in the study if subjects decide not to participate in Part D. If the next annual visit is in more than 6 months, these subjects will be assessed again at the next annual visit and undergo all assessments included in an annual visit. This will serve as their EOS assessment and will conclude their participation in the study if subjects decide not to participate in Part D. If the Part C EOS visit (at completion of the trial) is > 6 months from the last annual visit, this visit will serve as the EOT/EOS site visit, will include all annual assessments and will end their participation in the study.
- 5 Adult subjects who cannot receive non-flare-up-based treatment will only undergo annual assessments (clinical laboratory tests will not be performed).
- 6 Subjects with open epiphyseal growth plates at the most recent assessment will be evaluated at Months 6, 12, 18, 24, 30, 36, 42, 48, 54, 60, 66 and 72. As the linear growth assessments cannot be performed remotely, all assessments scheduled at these time points will be performed at the clinical site. Limb/joint AEs in these subjects will be evaluated by clinical and radiographic assessments deemed appropriate by the Investigator. Once a subject has achieved 100% skeletal maturity (confirmed by radiography as complete closure of the growth plate), knee and hand/wrist radiographs will no longer be required. If 100% skeletal maturity is not achieved at both locations, then only the location that is still maturing would need to be monitored. In addition, once a subject is 18 years old, linear growth assessments in triplicate and knee height will no longer be required.

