### **7.2.3 Body Weight and Linear Growth Assessments**

For subjects from Part B continuing non-flare-up-based treatment into Part C, body weight will be documented every 3 months (Months 3, 6, 9, 12, 15, 18, 21, 24, 27, 30, 33, 36, 39, 42, 45, 48, 51, 54, 57, 60, 63, 66, 69 and 72).

For subjects from Part B starting non-flare-up-based treatment during Part C, body weight will be documented at Part C Screening and every 3 months (Months 3, 6, 9, 12, 15, 18, 21, 24, 27, 30, 33, 36, 39, 42, 45 and 48).

For subjects receiving flare-up-based treatment, body weight will be recorded at Flare-up Cycle Safety Day 1 and every 12 weeks thereafter during safety assessments until treatment of the last flare-up or traumatic event in the flare-up cycle is completed.

Subjects from Part B continuing non-flare-up-based treatment into Part C with open epiphyseal growth plates at the most recent assessment will have linear growth assessments (in triplicate) by stadiometer and knee height measurements (in triplicate) at Months 6, 12, 18, 24, 30, 36, 42, 48, 54, 60, 66 and 72.

Subjects from Part B starting non-flare-up-based treatment during Part C that are under the age of 18 years and who enrolled with open epiphyseal growth plates at the most recent assessment will have linear growth assessments (in triplicate) by stadiometer and knee height measurements (in triplicate) at Screening. Subjects with open epiphyseal growth plates will also be evaluated at Months 6, 12, 18, 24, 30, 36, 42, and 48.

For subjects in Part D, body weight will be documented at Year 1 and Year 2 post last dose of study treatment. Subjects in Part D will have linear growth assessments (in triplicate) by stadiometer and knee height measurements (in triplicate) at Year 1 and Year 2 post last dose of study treatment.

Once a subject is 18 years old, triplicate linear growth and knee height assessments will no longer be required. In Part D subjects will stop participation once they reach 18 years of age.

Linear growth measurements will be performed by trained and qualified study personnel. The stadiometric measurement instructions will include practices that reduce measurement error including calibration of equipment, proper subject positioning, and measurement capture. The same examiner should be used whenever possible to standardize the performance of procedures and minimize the inter-examiner variability. Measurement of knee height will also be standardized.

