#### Study Visits and Assessments

- 1) **For subjects aged under 14 years that are still participating in the study but not currently receiving palovarotene treatment as per the global partial clinical hold or for any other reason**, they will complete Part C EOT/EOS and be invited to participate in Part D and undergo assessments outlined in [Table 4](#).
- 2) **For subjects aged 14 years and older who are being considered for re-starting palovarotene treatment but have NOT yet re-started**, the following minimum assessments are to be done via remote monitoring (video conference/phone calls) by the Investigator (or delegated study staff):
  - a. Chronic visits every 3-6 months (per protocol): assess for childbearing status (females only) and pregnancy prevention measures, CAJIS, ConMeds, adverse events, review subject diary, PROMIS Global Health Scale\*, FOP-PFQ\* (\*assessments that can occur remotely but not required as these are not essential to ensure subjects' safety)
  - b. For females of childbearing status: if pregnancy testing did not continue monthly per protocol post the study drug interruption then at a minimum a self-administered urine pregnancy test is to be done within 4 weeks before re-starting palovarotene treatment.
  - c. All subjects should have laboratory assessments (hematology, biochemistry, urinalysis) within 4 weeks before re-starting palovarotene treatment.
  - d. All subjects who were skeletally immature at the last assessment will have a hand-wrist and knee radiographs within 12 weeks before re-starting palovarotene treatment. For on-treatment subjects who have not reached at least 90% skeletal maturity radiograph assessments should continue per protocol either on site or remotely

Site staff will also assess the subject's ability to restart remotely.

3) **For subjects 14 years and over that plan to reinitiate dosing, once dosing is reinitiated following the required approvals for restart (Ethics Committee and Competent Authority), the following minimum assessments that cannot be performed via remote monitoring must be performed either at the clinical site, at the subject's home (by Symphony nursing) or at a local medical facility in order for the Investigator to adequately monitor the safety of subjects:**

- a. Via remote monitoring (telephone or video conferencing) by Investigator (or delegated study staff):

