  - i. Chronic visits (per protocol schedule every 3 and/or 6 months): C-SSRS, assess for childbearing status (females only) and pregnancy prevention measures, CAJIS, ConMeds, adverse events, PROMIS Global Health Scale\*, FOP PFQ\* (\*assessments that can occur remotely but are not required as these are not essential to ensure subjects' safety), study drug dispensing
  - ii. Flare up visits (per protocol schedule): C-SSRS, ConMeds, adverse events, study drug dispensing
- b. Via home visit by Symphony nursing/local assessment
  - i. Chronic visits per protocol schedule (every 3 and/or every 6 months): body weight, vital signs, hematology, biochemistry, urinalysis, self-administered pregnancy test (monthly), ConMeds, adverse events, review subject diary
  - ii. Flare up visits (per protocol schedule): vital signs, body weight, hematology, biochemistry, urinalysis, self-administered pregnancy testing, ConMeds, adverse events, review subject diary

4) **Based on the known safety profile of palovarotene to date in FOP patients, the following assessments can be postponed as determined by the Sponsor and individual site Investigators, as they do not constitute assessments where a safety concern has been raised.**

The below assessments were also deemed acceptable to postpone by the DMC chair.

- a. To date low dose whole-body CT has not indicated a safety concern of avascular necrosis of the hip. Any concerns for avascular necrosis of the hip based on clinical assessment should be followed up;
- b. For subjects who have reached at least 90% skeletal maturity radiograph assessments may be postponed given the low risk of early growth plate closure as well as growth plate abnormalities;
- c. Linear height and knee height (Subjects 14 years and older are at or near adult height indicated by skeletal maturity of at least 90%);
- d. ECG (FOP patients can have ECG abnormalities, ECG changes noted in subjects on Palovarotene were similar to those seen in the untreated subjects in the Natural History Study. Clinical concerns of abnormal ECG findings should continue to be followed);
- e. Hearing evaluation (As a class, retinoids can cause abnormal hearing. Evaluation should be performed if there is clinical concern);
- f. Physical exam (Palovarotene has been shown to cause retinoid skin reactions which can be assessed remotely)

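### Section 7.7 item 4c lets height measurements be postponed because subjects aged 14 or over are taken to be at least 90% skeletally mature, but item 2d provides for treated subjects below 90%

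*Protocol*

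**What the plan says.** Section 7.7 (Temporary Measures) sets out what may and may not lapse during the pandemic. Four parts matter here.

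- **Item 4, lead sentence.** It says that "the following assessments can be postponed as determined by the Sponsor and individual site Investigators", on the ground that none of them is an assessment that has raised a safety concern.
- **Item 4b, radiographs.** The permission depends on the individual subject's maturity: "For subjects who have reached at least 90% skeletal maturity radiograph assessments may be postponed".
- **Item 4c, linear and knee height.** No condition is set. The parenthesis gives a reason instead: "Subjects 14 years and older are at or near adult height indicated by skeletal maturity of at least 90" per cent.
- **Item 2d, second sentence.** Within the block for subjects aged 14 and older it states: "For on-treatment subjects who have not reached at least 90% skeletal maturity radiograph assessments should continue per protocol", on site or remotely.

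Sections 3.1 and 3.2 say that treatment will not be restarted in children under 14. Section 7.2.3 ends height monitoring at adulthood: "Once a subject is 18 years old, triplicate linear growth and knee height assessments will no longer be required". Section 7.7 of PVO-1A-204 carries the same items 2d, 4b and 4c.

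**The concern.** Item 4c justifies a relaxation of monitoring with a claim about a whole age group, and item 2d shows that the authors did not regard that claim as universally true. The subjects to whom it does not apply are those still growing while on drug. Section 3.2 calls premature physeal closure a serious identified risk. Section 1.1.3.2 explains that linear and knee height are measured to assess growth in subjects with open epiphyses. A site that reads item 4c literally could leave out the height of a 15-year-old below 90% maturity who is standing in the clinic for a radiograph, and would be within the protocol in doing so.

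**Working it through.** No figure in the plan is in question, so the check is a comparison of texts.

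1. **Who is on treatment.** Subjects under 14 had to interrupt drug on 4 December 2019 and will not be restarted (Section 3.1). Any on-treatment subject under the current text is therefore 14 or older.
2. **Who item 2d's second sentence covers.** On-treatment subjects below 90%. By step 1 they are aged 14 or over.
3. **What item 4c asserts.** Subjects aged 14 or over have at least 90% maturity. For the subjects in step 2 this is false by definition.
4. **Can the protocol's definitions produce such subjects?** Yes. Section 3.1 defines skeletal immaturity for dosing as under 18 years with less than 90% maturity on hand/wrist radiography, so a subject of 14 to 17 can qualify.
5. **Upper age limit.** Triplicate linear growth and knee height stop being required at 18 (Section 7.2.3; Table 1, footnote 6). The conflict therefore concerns ages 14 to 17 only.
6. **Could the parenthesis in 4c be read as a condition?** Only with strain. Item 4b, directly above it, shows how the authors write a condition. Item 4c uses a statement of fact about an age group.
7. **Does another item protect heights?** Item 3's minimum list for subjects who have restarted contains no height measurement, so item 4c is the operative text. Item 4b with item 2d preserves radiographs below 90%; nothing equivalent preserves heights.
8. **Is the gap avoidable in practice?** In part. Table 1, footnote 6 says linear growth cannot be measured remotely. Item 2d, however, allows radiographs on site, and at such a visit height could be measured with no additional journey.

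The rationale in the Amendment 8 summary of changes agrees with item 2d. Maturity is to be assessed in subjects aged 14 "years re-initiating treatment in order to ensure appropriate safety follow up as well as determine if weight-based dosing is required". Weight-based dosing stops at 90% (Section 3.1), so the question is open only if some subjects of that age might be below it. This is supporting context; steps 1 to 3 are sufficient without it.

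**The case against.** The best defence is practical. Radiographs can be taken at a local facility; heights need the clinical site, trained staff, calibrated equipment and preferably the same examiner (Section 7.2.3). Keeping radiographs while letting heights slip is a reasonable pandemic choice even below 90%, and Section 7.7 records that the DMC chair found the listed postponements acceptable. That stands for subjects who do not travel. It does not cover those who come to the site anyway, and it is not the reason that item 4c gives. The chair's acceptance does not make the stated premise true.

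The safeguards are also real. Postponement is permitted, not ordered. The investigator can require an assessment on clinical concern. Dosing feasibility is decided subject by subject, and each subject has a risk mitigation assessment. Dose modification under Section 6.5 applies with or without growth deceleration. Item 6 lists linear and knee height among the assessments to be done once site visits resume. Together these limit the consequence but leave the contradiction in place.

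Two stronger readings are tempting and are not supported.

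- A reader might infer that item 2d's first sentence, "All subjects who were skeletally immature at the last assessment will have a hand-wrist and knee radiographs", is a second contradiction. It need not be. The protocol uses immaturity in two senses: below 90% for dosing, and short of 100% for radiographic follow-up and Part D. A subject at 90 to 99% may be immature in the second sense and still fit item 4c.
- A reader might try to count missed heights from the interval between the April 2020 addendum and Amendment 8. Those dates do not measure time on drug, since subjects were awaiting approvals to restart. Nor do they bound the measures, which last as long as local pandemic warnings do.

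**Conclusion.** The contradiction holds, and it rests on item 4c against the second sentence of item 2d, together with the rule that dosing is not restarted under 14. It is minor. It concerns subjects aged 14 to 17, below 90% maturity and on drug, whose number the protocol does not give and which may be small or even zero: item 2d provides for such subjects without saying that any exist. What is lost is at most a deferral of growth measurements, at the discretion of sponsor and site, while radiographs continue. The number of heights deferred cannot be derived from the document. No efficacy endpoint or analysis is affected. Because the measures are open-ended, correcting the text still has value for later visits.

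**What to change.** In Section 7.7 item 4c, replace the age-based reason with the threshold already used in item 4b: linear and knee height may be postponed in subjects who have reached at least 90% skeletal maturity. Add one sentence: below 90%, linear and knee height are measured whenever radiographs are done at the clinical site; otherwise investigator judgment and the item 6 catch-up apply. Make the same change in Section 7.7 of PVO-1A-204.

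The cost is one reworded and one added sentence in each protocol, and a few extra measurements at site visits that are already taking place. Subjects whose radiographs are taken locally would be handled as they are now, so no additional travel is imposed.

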**5) End of Treatment/End of Study Assessments:**

- a. The following assessments should be performed via remote monitoring (telephone or video conferencing) by Investigator (or delegated study staff):
  - i. C-SSRS, assess for childbearing status (females only) and pregnancy prevention measures, CAJIS, Con-Meds, adverse events, PROMIS Global Health Scale, FOP PFQ
- b. The following assessments should be performed at the subject’s home (by Symphony nursing) or at a local medical facility: Body weight, vital signs, hematology, biochemistry, urinalysis, pregnancy test (monthly), ConMeds, adverse events, review subject diary

**6) Once on-site visits resume, the following assessments should be performed on site as well as any assessment that was not obtained via remote monitoring or Symphony nurse:**

- a. X-rays, Whole-Body CT, Linear and Knee Height, Physical Exam, ECG.

**7) Informed Consent/Subject Communication:** In consultation with their site IRB/EC, Investigators are required to inform subjects of the temporary changes (during the COVID-19 global pandemic) to the study conduct and monitoring plans that could impact them and their willingness to continue participation in the trial. The method of communication to subjects (e.g., email, phone call, information letter) and documentation of subject/caregiver acknowledgement is to be performed and documented in accordance with local regulations/EC requests and guidance. All contacts with subjects must be filed in the source records.

A risk mitigation assessment will be performed for each subject at the site in order to determine how their participation may be impacted. Sites must ensure that appropriate measures are taken to ensure the safety of FOP subjects in light of the ongoing COVID-19 pandemic, taking into consideration local Ethics Committee and Competent Authority guidance, as well as the ability of individual Investigators and sites to adequately monitor subject safety.

**8. STATISTICAL AND ANALYTICAL PLANS**

This study is intended to assess whether a non-flare-up-based dosing regimen, combined with higher doses during times of flare-ups, will result in a lower incidence of new HO formation. As this is an open-label study with no comparator arm, use of subject data from Study PVO-1A-001 (Natural History Study [NHS]) will form the basis for a control arm. Additional analysis of the flare-up-based treatment regimen will be described in the Statistical Analysis Plan (SAP).

A summary of the general methods and strategies for analysis is provided in the sections below. A more comprehensive SAP will be written that will describe the manner in which the analysis will be performed.

## 8.1 General Methods

For purposes of assessing the efficacy of the non-flare-up-based dosing regimen, low-dose WBCT imaging data from Part B (after Amendment 3) and Part C will be combined.

## 8.2 Sample Size

The new HO volume data as assessed by low-dose WBCT scan, excluding head, from Part B (after Amendment 3) and Part C will be combined. The sample size was fixed by the number of subjects enrolled in Part B and was not based on power calculations.

## 8.3 Study Populations

The following populations will be analyzed under Amendment 4 and subsequent amendments:

- The Full Analysis Set (FAS) includes all enrolled subjects having a baseline HO volume measurement and at least one post-baseline HO volume measurement in the PVO-1A-202 study. For efficacy comparisons to the NHS, the FAS will also include subjects enrolled in the NHS with available baseline and at least one post-baseline HO volume measurements.
- The Per-Protocol Set (PPS) is a subset of the FAS including subjects with no major protocol deviations that are expected to interfere with assessments of the primary endpoint, and with at least 80% compliance to the study drug regimen. For efficacy comparisons to the NHS, the PPS will also include subjects in the NHS with available baseline and at least one post-baseline HO volume measurements and with no major protocol deviations that are expected to interfere with assessments of the primary endpoint.
- The Safety Analysis Set (SAS) includes all enrolled subjects receiving at least one dose of palovarotene in the PVO-1A-202 (after Amendment 3). For safety comparisons to the NHS, the SAS will also include subjects enrolled in the NHS with available post-baseline follow-up.
- The Pharmacokinetic Analysis Set (PAS) is a subset of the SAS including subjects with evaluable pharmacokinetics data.

## 8.4 Baseline and Disease Characteristics (including Medical History)

Baseline and disease characteristics will be tabulated descriptively (eg, number and percentage of subjects for each category for categorical parameters, and the number, mean, standard deviation, and range for continuous parameters).

## 8.5 Subject Disposition

Subject disposition will be listed and summarized.

## 8.6 Extent of Exposure

The extent (duration) of exposure will be determined from the date of first dose of study drug through the date of last dose of study drug. For times during which subjects are receiving

flare-up-based treatment, tabulation of the number of days at the higher dose(s) will be presented. An assessment of the proportion of subjects who are able to tolerate the higher doses will be performed.

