### 3.2 Study Rationale

Prior to Protocol Amendment 3, this study followed subjects who rolled over from Study PVO-1A-201 and provided open-label active treatment to any subject who experienced a subsequent flare-up. This allowed for the collection of long-term efficacy and safety data of palovarotene (10 mg for 14 days, followed by 5 mg for 28 days), and provided active treatment to all subjects experiencing eligible flare-ups including those who were randomized to placebo during Study PVO-1A-201. Clinical data obtained from the Phase 2 interventional studies, as well as recent animal pharmacology data, have contributed to the understanding of FOP disease progression, the risk factors leading to HO formation, and the potential utility of palovarotene in preventing HO formation.

Fibrodysplasia Ossificans Progressiva is a disease that is characterized by HO that may develop spontaneously or after soft tissue trauma, vaccinations, or influenza infections. The HO accumulates throughout life, resulting in segments, sheets, and ribbons of extra bone throughout the body and across joints, progressively restricting movement. While HO formation may be preceded by signs and symptoms of a flare-up such as pain, swelling, redness, decreased range of motion, stiffness, and warmth, the biological process that results in the formation of HO may begin before the onset of symptoms. Thus, the optimal treatment for FOP might be similar to other chronic diseases that are characterized by acute exacerbations/relapses, followed by variable-length periods of apparent disease quiescence (eg, relapsing/remitting multiple sclerosis) during which clinical symptoms are not observed.

It is hypothesized that daily treatment in the absence of flare-up symptoms, which will ensure exposure to palovarotene when the endochondral process starts, together with increasing the dose immediately upon symptom onset (the chronic flare-up regimen), may be a better approach than treating only when clinical symptoms are present (the flare-up only regimen). Under Protocol Amendment 3, adult subjects initiated non-flare-up-based daily treatment with palovarotene, which is extended to the Pediatric Cohort subjects under Protocol Amendments 4 and 5. In addition, subjects experiencing an eligible intercurrent flare-up will restart flare-up-based dosing in order to continue exposure to palovarotene and provide an optimal treatment for all flare-ups that may occur during the study.

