### **8.8.1 Adverse Events**

Adverse events will be classified using the MedDRA coding dictionary. Adverse event severity will be assessed and reported according to criteria defined in the protocol (mild, moderate, severe).

Adverse events known to be associated with retinoids (eg, mucocutaneous events) will be further graded according to CTCAE, Version 4.03, 14 June 2010.

Tabulations will include an overall incidence of at least one AE, incidence within body system, and incidence by preferred term. Each subject may only contribute once (ie, first occurrence) to each of the incidence rates, regardless of the number of occurrences. Incidences (denominators and percentages) for selected gender-specific AEs will be adjusted by the number of males or females, as appropriate.

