#### **8.6 Extent of Exposure**

The extent (duration) of exposure will be determined from the date of first dose of study drug through the date of last dose of study drug. For times during which subjects are receiving flare-up based treatment, tabulation of the number of days at the higher dose(s) will be presented. An assessment of the proportion of subjects who are able to tolerate the higher doses will be performed.

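### Section 8.6 counts exposure from first to last dose date, so off-drug gaps in an intermittent dosing design are reported as exposure

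*Protocol*

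**What the plan says.** Section 8.6 of PVO-1A-202 states that duration of exposure "will be determined from the date of first dose of study drug through the date of last dose of study drug". Section 8.6 of PVO-1A-204 uses the same rule. Neither mentions interruptions or gaps between courses. Both add that, for periods on flare-up treatment, "tabulation of the number of days at the higher dose(s) will be presented". No matching count is stated for days at 5 mg or days off drug.

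Elsewhere the protocol describes time off drug that can fall between a first and a last dose:

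- **Part B, paediatric subjects.** Section 1.1.3.2 says daily dosing in Part B was for subjects with at least 90% skeletal maturity. Section 3.2 says daily treatment began in adults, "which is extended to the Pediatric Cohort subjects under Protocol Amendments 4 and 5". Before that, paediatric subjects took drug only for flare-ups.
- **Restart at age 14 and over.** Section 7.7 sets out assessments for subjects "who are being considered for re-starting palovarotene treatment but have NOT yet re-started". The length of the interruption is not given.
- **Prohibited co-medication.** Section 5.6.1 has drug stopped during a strong CYP3A4 inhibitor or a tetracycline, with a wash-out before restart.
- **Growth plate findings.** Section 6.5 lists interruption among the options.

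Section 8.3 limits the safety set to subjects dosed after Amendment 3. Section 8.6 does not say whether the first dose is the first ever or the first after Amendment 3.

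**The concern.** A first-to-last-dose span is a fair summary when dosing is continuous. Here it credits children on flare-up-only courses, and anyone who restarts, with months in which they took nothing. The stated totals would then describe time since first dose rather than time on drug.

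The error is not spread evenly. It is largest in paediatric subjects with a flare-up-only history, a group that includes the skeletally immature subjects whose growth plates are the main safety concern (sections 1.1.3.2 and 3.2).

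The higher-dose tabulation does not repair this. If a reader subtracts the higher-dose days from the span, what remains mixes 5 mg days with days off drug, and the off-drug days look like chronic dosing.

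**Working it through.** The protocol states no exposure total or exposure-based rate, so there is no figure to reproduce. The check is how far the definition can move the reported duration.

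**Formula.** Let S be the days (or months) from first to last dose and G the time off drug inside that span. Exposure is overstated by the factor S / (S − G).

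**Inputs from the protocol.** A flare-up course is 28 + 56 = 84 days (section 3.1). Two treated flare-ups per year are expected (section 7.2.6). Part B lasted up to 24 months, and daily treatment runs up to 48 or 72 months by cohort (section 3.1).

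**Assumed inputs.** Gap lengths of 3 to 18 months. Flare-ups evenly spaced, courses neither extended nor restarted.

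**(a) One interruption followed by restart**

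| Gap (months) | 48-month span | 72-month span |
|---|---|---|
| 3 | 48/45 = 1.07 | 72/69 = 1.04 |
| 6 | 48/42 = 1.14 | 72/66 = 1.09 |
| 12 | 48/36 = 1.33 | 72/60 = 1.20 |
| 18 | 48/30 = 1.60 | 72/54 = 1.33 |

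**(b) Flare-up-only dosing over 24 months**

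- Two per year: 4 courses, 182.6 days apart. Span = 3 × 182.6 + 84 = 632 days. On drug = 4 × 84 = 336 days. Factor = 632/336 = 1.88. The other 296 days involve no drug.
- One per year: 2 courses, 365.25 days apart. Span = 365.25 + 84 = 449 days. On drug = 168 days. Factor = 449/168 = 2.67. The other 281 days involve no drug.

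**(c) Dilution once daily dosing follows.** Suppose the 24 months in (b), 730.5 days with the first course on day 1, are followed at once by uninterrupted daily dosing.

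- 24 months of daily dosing: span 1461 days; on drug 336 + 730.5 = 1066.5 or 168 + 730.5 = 898.5 days. Factor 1.37 or 1.63.
- 48 months of daily dosing: span 2191.5 days; on drug 336 + 1461 = 1797 or 168 + 1461 = 1629 days. Factor 1.22 or 1.35.

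The factors in (b) therefore describe the flare-up-only period; over a longer record they shrink but do not vanish. Extended or restarted courses would add on-drug days and shrink them further.

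**(d) Effect on planned AE figures.** Section 8.8.1 counts subjects: "Each subject may only contribute once (ie, first occurrence) to each of the incidence rates, regardless of the number of occurrences". That proportion contains neither S nor G, so it changes by 0% in every case above.

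**The case against.** The strongest reply is that nothing the protocol plans to report about risk depends on this duration. A reader might infer that risk per unit of exposure is understated. The documents do not support that: no rate per unit of exposure is planned, and the subject-level incidence in section 8.8.1 does not use the section 8.6 duration. If someone did divide events by the span, the rate would be low by G/S: 6% to 38% in the 48-month column of (a), and 47% or 63% in (b). That is conditional on a step the protocol does not take.

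A reader might also fault section 8.8.1 for lacking event rates per patient-year, since follow-up differs by cohort and section 8.3 provides for safety comparisons with the natural history study. Exposure-adjusted rates are ordinary content for a statistical analysis plan (SAP). Section 8 calls itself a summary and defers to a fuller SAP, and section 8.8.1 does not exclude such rates. Their absence here is not a defect.

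Three further replies hold in part.

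- Days at flare-up doses are tabulated, and section 1.1.3.2 links that regimen to a higher risk of premature epiphyseal fusion. This covers part of the need, but not the split between 5 mg and no drug.
- For subjects under 14 who never restart, the hold from 04 December 2019 falls after the last dose and is not counted. The hold inflates nothing for them.
- Part A precedes the dosing that defines the safety set. But section 8.3 decides who is in the set, not when the exposure clock starts, so a Part A first dose is not clearly excluded.

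The definition itself cannot be left to the SAP in the same way. Section 8.6 states it positively, and a SAP that follows the protocol inherits it.

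**Conclusion.** The point stands as a fault in the exposure definition. As written, section 8.6 in both protocols reports off-drug time as exposure, in a study whose own rules create off-drug time between first and last dose.

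The size depends on assumptions. It is about 1.07 to 1.6-fold for a single gap of 3 to 18 months in 48 months, and about 1.9 to 2.7-fold over 24 months of flare-up-only dosing at two or one flare-ups per year. It is smaller once a long period of daily dosing follows. Gap lengths and flare-up spacing are not in the protocol, so these figures illustrate the range and do not estimate the actual error.

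No stated AE figure is wrong because of this, and no claim of understated risk follows. The correction is still worth making, because exposure totals are read on their own and are the natural denominator for any later rate.

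**What to change.** In section 8.6 of PVO-1A-202 and PVO-1A-204:

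- Define exposure as the sum of days on drug, taken from the dosing diary and from dispensing and return records, net of interruptions and gaps between courses.
- Split it by regimen: 5 mg (or weight equivalent), high flare-up dose and low flare-up dose.
- Report the first-to-last-dose span alongside, labelled as a span.
- State which first dose starts the clock for the post-Amendment 3 safety set.
- Require net on-drug days as the denominator of any exposure-adjusted rate, should the SAP include one.

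No change to section 8.8.1 is needed. No new data are needed either: section 6.4 already has the daily dose recorded in the diary, and section 6.7 tracks drug dispensed and returned. The cost is a wording change, one derived exposure dataset and smaller stated exposure totals.
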